10.4.5. Statistical Analysis of Primary Endpoint(s)

Analysis of the Primary Endpoint to test the hypothesis will be performed using [REDACTED] [REDACTED]. Missing data at the time of analysis will not be imputed.

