2.4 Statistical Hypotheses

The registry is designed to statistically test the hypothesis that the Target Vessel Patency at 12 months (Primary Performance Endpoint) in both FEVAR and BEVAR populations of subjects is greater than 77%. The hypothesis will be tested separately in the two cohorts (FEVAR and BEVAR), using the subjects with imaging results available for the 12 months visit. The binomial exact test will be used with a one-sided 2.5% level of significance to test the null hypothesis.

The statistical hypothesis is specified as follows:

H0: $P \leq 77\%$

HA: $P > 77\%$

Alpha= 0.025 (one-sided)

Whereas P is the probability of maintaining Target Vessel Patency at 12 months.

The ITT population will be used to perform this test.

[REDACTED]

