Site may need to send anonymized source documentation to CRO related to the events that need to be adjudicated by CEC. This committee will operate under pre-specified procedures as outlined in its charter. The frequency of data review and other roles and responsibilities of the committee will be

- Site Enrollment Restrictions (if applicable)

Up to 15 sites in Europe will be required to enroll a minimum of 220 patients that have had treatment with GORE® [REDACTED]® [REDACTED] when used as a Bridging Stent with Branched and Fenestrated Endografts in the Treatment of Aortic Aneurysms Involving the Renal-Mesenteric Arteries.

Each site cannot contribute to more than 10% of the total patient for each cohort without sponsor approval, with a maximum of 20% of total enrollment for a single site.

- Core lab (if applicable)

The Core Lab will perform assessments of imaging modalities according to objective process and standard procedures completed by trained and qualified personnel.

Medical imagery will be transmitted to the Core Lab using the secure, web portal functionality of the [REDACTED] System. Imaging submitted through the portal will be stripped of personal health information and replaced with appropriate registry subject identifiers in automated, systemic fashion. Recipients will process received imaging according to their standard operating procedures or registry-specific processes. Completed assessments and measurements will be reported directly in the EDC system and this data is considered source data.

- Handling of missing data

All effort will be made to minimize the missing data, however, the data not available will be treated as missing in the study and the analysis will be conducted on the available data.

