5.0 Statistical Analyses

[figure not shown]
Analysis Populations

- The registry population will consist of patients that have had treatment with GORE® [REDACTED]® [REDACTED] and that meet the registry eligibility criteria.

CONFIDENTIAL INFORMATION

Page 10 of 15

Timing of Analyses

The analysis to test the primary hypothesis will be conducted once all subjects have completed their 12 Month follow-up, data has been entered and cleaned in the EDC system. Subjects with a visit within 90 days of the annual time frames (i.e., 275 – 455 for 12 Month visit) would be considered for analysis of the annual outcomes. In case of the multiple visits within the interval, the visit closest to and preceding the annual time point would be considered for the determination of the outcomes.

[REDACTED]
The subject follow-up will continue for five years, and the final analysis will be done once all subjects have completed five-year follow-up. [REDACTED]

[REDACTED] No interim analysis for the early termination of registry is planned due to the post marketing usage of the [REDACTED] Stent Graft and retrospective nature of the enrollment. In addition, once the primary analysis has been performed and hypothesis tested, further analyses may also be performed as needed for annual reports, presentations and publications based on interim data or at any other time at the discretion of Gore.

CONFIDENTIAL INFORMATION

Page 11 of 15

Analysis Populations

Intent-to-Treat (ITT) dataset will consist of all enrolled patients meeting the inclusion / exclusion criteria and treated at least one vessel with the [REDACTED] Stent Graft. A subset of the ITT dataset will be further identified of subjects with all vessels treated with [REDACTED] and another subset with all vessels treated with [REDACTED] only. ITT dataset will be used for the analysis of the primary and secondary endpoints. Similarly, per vessel analysis will be performed with all three datasets after identifying each vessel treated by [REDACTED] and also of the vessels treated without [REDACTED]

[REDACTED]

Pooling of Data

All sites in the registry will follow a common protocol and the data will be monitored to assure compliance. The data collection and handling procedures will be the same at all registry Sites. As such, there is no concern in pooling data from different sites together for analysis.

[REDACTED]

Statistical Analysis of Primary Endpoint(s)

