Analysis of the Primary Endpoint to test the hypothesis will be performed using binomial exact test using one-sided 2.5% level of significance.

All subjects with follow-up visit and imaging results available from 9 to 15 months will be included in the primary analysis. Subjects with the loss of Target Vessel Patency earlier than 15 months will also be included in such analysis and considered as failures regardless of the timing and availability of another visit between 9 to 15 months.

[REDACTED]

Statistical Analysis of Secondary Endpoint(s)

[REDACTED]

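### The visible SAP rule for the primary test does not estimate 12-month patency, and its analysis set contradicts SAP 2.4; the direction of the bias depends on how completely losses are recorded

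*SAP*

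**What the plan says.** - **Target.** SAP 2.3 and Protocol 3.4.2 set the primary endpoint as patient-level target vessel patency at 12 months. SAP 2.4 adds: "Whereas P is the probability of maintaining Target Vessel Patency at 12 months". SAP 2.3, Table 1, defines primary patency as uninterrupted, lost by an occlusion or by a procedure to maintain patency.
- **Analysis set, first description.** SAP 2.4 and Protocol 10.1 test each cohort "using the subjects with imaging results available for the 12 months visit", and also name the ITT population.
- **Analysis set, second description.** SAP 5.0, under the primary endpoint, says that subjects with a visit and "imaging results available from 9 to 15 months will be included in the primary analysis". It then adds "Subjects with the loss of Target Vessel Patency earlier than 15 months", who are "considered as failures regardless of the timing and availability of another visit between 9 to 15 months".
- **Visit selection.** SAP 5.0, Timing of Analyses, defines the 12-month visit as day 275 to 455. With several visits in the window, "the visit closest to and preceding the annual time point would be considered for the determination of the outcomes". Patency is not exempted.
- **Missing data.** SAP 4.0: "the data not available will be treated as missing in the study and the analysis will be conducted on the available data". Protocol 10.4.5: "Missing data at the time of analysis will not be imputed".
- **Data source.** Follow-up and imaging follow local standard of care, and phone contact is accepted (Protocol 5 and 5.11).

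**The concern.** A window of 90 days either side is sensible when imaging is not protocol-driven. The difficulty is that the two outcomes are admitted on different terms.

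- A loss counts at any time up to month 15 and needs no window image. A patient shown patent at day 370 who occludes at day 440 is a 12-month failure.
- A success needs a window image, which may date from month 9. A patient without a window image who is patent at two years with no recorded loss is dropped, although that image shows uninterrupted patency at day 365.

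This rule decides the registry's only formal hypothesis, separately in FEVAR and BEVAR. A cohort that meets the goal at 12 months could fail the test. If losses go unrecorded, a cohort that does not meet the goal could pass. The visible text does not let a reader tell which has happened.

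**Working it through.** **Inputs from the documents.** Goal 77%, exact binomial, one-sided 2.5% (SAP 2.4). FEVAR 100, BEVAR 120 (Protocol 4.1). Allowance for missed visits 10% (Protocol 10.4.3).

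**Assumptions.** Planned rates and power are redacted (Protocol 10.2 and 10.3), so the sample size cannot be reproduced. I assume 12-month patency P12 = 90% for power, with 88% and 92% as a range. Patency follows S(t) = P12^(t/12) (constant hazard) or S(t) = P12^√(t/12) (front-loaded losses), t in months.

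**1. The plan's own figures.** 365 ± 90 gives day 275 to 455, as stated, or about months 9 to 15. The exact test needs 86/100 and 102/120 successes, with actual size 0.0177 and 0.0205.

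**2. What is tested at a true 77%, all losses recorded.** S(15) = 0.77^1.25 = 0.7213. If 10% of patent patients lack a window image while every failure stays in:

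0.9 × 0.7213 / (0.9 × 0.7213 + 0.2787) = 0.6492 / 0.9279 = 0.700.

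The tested proportion is 0.72 or 0.70, not 0.77.

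**3. Power at an assumed 90%, all losses recorded.** S(15) = 0.90^1.25 = 0.8766 (front-loaded 0.8889). With 10% of patent patients unimaged: 0.9 × 0.8766 / (0.9 × 0.8766 + 0.1234) = 0.8647, on about 91 and 109 patients. Rows with missing images average over the random number included.

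| Rule | n=100 | n=120 |
|---|---|---|
| True 12-month status, none missing | 93% | 97% |
| All losses to month 15, none missing | 75% | 85% |
| Same, front-loaded losses | 86% | 93% |
| True 12-month status, 10% missing at random | 90% | 95% |
| SAP 2.4 set, losses to month 15, 10% missing at random | 70% | 79% |
| SAP 5.0 set, 10% of patent patients unimaged | 59% | 68% |

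At n=100 the last three rows separate the two drivers: the month-15 cut-off takes 90% to 70%, and the one-sided inclusion takes 70% to 59%. Across assumed rates at n=100 with none missing, true 12-month status against all losses to month 15 is 78% against 48% at P12 = 88%, and 99% against 93% at 92%. Because every loss is taken as recorded, these falls are upper bounds.

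**4. The opposite direction: true 77%, losses after the image unrecorded.**

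- *Early images.* With all images at month 9, S(9) = 0.77^0.75 = 0.822. False success at n=100 is 19.6% if no later loss is recorded, 7.0% if a quarter are, and 1.9% if half are. With images spread over months 9 to 12 (mean 0.796) it is 6.6%, 2.6% and 0.9%. The tested rate returns to 0.77 when the recorded share of later losses is (0.8220 − 0.77)/(0.8220 − 0.7213) = 0.52 for month-9 images, and (0.7957 − 0.77)/(0.7957 − 0.7213) = 0.35 for months 9 to 12.
- *Occluded patients imaged less often.* With images uniform over months 9 to 15, mean patency is 0.7705. If 10% of patent and 20% of occluded patients lack the image and those losses are unrecorded: 0.9 × 0.7705 / (0.9 × 0.7705 + 0.8 × 0.2295) = 0.6935/0.8771 = 0.791, with false success 4.9%. At 10% against 30% it is 0.6935/0.8541 = 0.812, with 11.6%. With equal missingness the same image pattern stays at about 1.8%.

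**5. The two SAP 5.0 rules side by side.** Take a patient patent at day 340 and occluded at day 440. Timing of Analyses selects day 340: success. The primary-endpoint paragraph counts a loss before month 15: failure.

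**The case against.** **The window is declared, and counting losses to its end is an accepted convention.** That is fair, and the basis for the 77% goal is redacted, so nobody can show that the goal means day 365 exactly. But P is still written as a 12-month probability, and the convention does not explain why failures enter without an image and non-failures do not.

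**The specific rule overrides the general one.** This also stands. The primary-endpoint paragraph governs the primary test, so a reader should not infer that the test is undefined for the day-340/day-440 patient. What remains is a missing cross-reference.

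**A reader might infer that the rule is simply conservative, and therefore harmless.** The documents do not support that. Reinterventions and adverse events are collected (Protocol 5.10 and 9.1.3), which makes recorded losses plausible. But imaging is by local practice, phone follow-up is accepted, and death or withdrawal ends follow-up (Protocol 5.12 and 5.14), so silent occlusions can be missed. Step 4 shows that early images are not needed for the error to reverse. **Nor do the documents support the opposite inference**, that the rule inflates success: that needs losses to go largely unrecorded.

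**Redaction.** Text after both SAP 5.0 rules and in SAP 7 and 8 is blacked out. A sensitivity analysis may be there, and I do not claim that one is absent. The contradiction between SAP 2.4 and SAP 5.0 is in visible text.

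**Conclusion.** The point holds on two counts. The visible primary rule does not estimate the stated 12-month patency, and its analysis set is not the one in SAP 2.4 and Protocol 10.1. The main drivers are the one-sided inclusion and the month-15 cut-off for losses.

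The direction is conditional. With good recording of losses the test is conservative, with power at n=100 falling from 93% to between 75% and 59% under an assumed 90% and constant hazard, and less if losses are front-loaded. With poor recording it can be anti-conservative, at 4.9% to 19.6% false success in the extreme scenarios shown against a nominal 2.5%. Neither the timing of images nor the completeness of loss recording is given, so the net sign cannot be settled from the documents. The point should be fixed, but it does not invalidate the exact test.

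**What to change.** 1. **State one analysis set** in Protocol 10.1, SAP 2.4 and SAP 5.0. Remove the asymmetry by also including, as 12-month successes, patients without a window image who have no recorded loss and whose later image shows uninterrupted patency. Merely rewording SAP 2.4 to match SAP 5.0 would keep the asymmetry. If every unimaged patent patient were recovered, step 3 returns from 59% to 75% at n=100; that is the upper limit.
2. **In Timing of Analyses**, state that the visit-selection rule does not override a recorded patency loss.
3. **Keep the exact test and the pre-specified failure rule**, but label the result as patency through the 12-month window (to month 15). Unless the redacted text already provides it, report beside it a day-365 estimate in all ITT subjects of each cohort: interval-censored for losses first seen on imaging, with procedures entered at their date.
4. **Report per cohort** the successes resting only on an image before day 365, the failures without a window image, and the patients without a recorded loss who were dropped.

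**Cost.** Wording changes (a protocol amendment for 10.1), one table and three counts, from dates already collected. The day-365 estimate is approximate and cannot recover losses that are never recorded. In a simulation at a true 77%, with 10% of window images missing and a second-year image in 80% of patients, an interval-censored Weibull estimate ran from 0.747 to 0.775, against 0.698 to 0.797 for the SAP 5.0 rule. Plain Kaplan-Meier on detection dates reached 0.89 and should be avoided. Item 1 also leaves out patients without a window image whose loss is first seen after month 15; the day-365 estimate covers them.

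**Optional.** The primary count could stop treating as failures those losses dated after a patent image at or after day 365. This loosens a pre-specified rule on largely retrospective outcomes. With 10% of patent patients unimaged and images uniform over months 9 to 15, it lifts power at n=100 only from 59% to 65% unless the asymmetry is also removed.

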6.0 Interim Analyses and Safety Monitoring Analyses (if applicable)

No interim analysis is planned for early termination of the registry due to the retrospective study design.

CONFIDENTIAL INFORMATION

Page 12 of 15

7.0 Analysis Specifications

7.1

[REDACTED]

8.0

[REDACTED]

[REDACTED]

[REDACTED]

[REDACTED]

[REDACTED]

[REDACTED]

[REDACTED]

CONFIDENTIAL INFORMATION

Page 13 of 15

This figure is a 2D grayscale heatmap representing a probability density or signal distribution. The distribution is highly concentrated in several distinct regions, with the highest intensity (black) occurring in the central and upper-middle areas. The background is white, and the distribution is bounded by a dark gray border. The overall shape is roughly rectangular but with irregular, jagged edges, suggesting a complex underlying process or a noisy signal. The distribution is not uniform, with several peaks and valleys visible across the field.

10.0 Revision History

[REDACTED]	[REDACTED]	[REDACTED]	[REDACTED]
[REDACTED]	[REDACTED]	[REDACTED]	[REDACTED]
[REDACTED]	[REDACTED]	[REDACTED]	[REDACTED]
[REDACTED]	[REDACTED]	[REDACTED]	[REDACTED]

CONFIDENTIAL INFORMATION

Page 15 of 15
